8.2. Efficacy Assessments

Not applicable.

8.3. Safety Assessments

Planned time points for all safety assessments are provided in the [SoA](#). Unscheduled safety measurements may be obtained at any time during the study to assess any perceived safety issues.

8.3.1. Physical Examinations

A complete physical examination will include, at a minimum, head, ears, eyes, nose, mouth, skin, heart and lung examinations, lymph nodes, and gastrointestinal, musculoskeletal, and neurological systems.

A brief physical examination will include, at a minimum, assessments of general appearance, skin, the respiratory and cardiovascular systems, and participant-reported symptoms.

Physical examinations may be conducted by a physician, trained physician's assistant, or nurse practitioner as acceptable according to local regulation.

Height and weight will also be measured and recorded as per the [SoA](#). For measuring weight, a scale with appropriate range and resolution is used and must be placed on a stable, flat surface. Participants must remove shoes, bulky layers of clothing, and jackets so that only light clothing remains. They must also remove the contents of their pockets and remain still during measurement of weight.

Physical examination findings collected during the study will be considered source data and will not be required to be reported, unless otherwise noted. Any untoward physical examination findings that are identified during the active collection period and meet the definition of an AE or SAE ([Appendix 3](#)) must be reported according to the processes in Sections [8.4.1](#) to [8.4.3](#).

8.3.2. Vital Signs

8.3.2.1. Blood Pressure and Pulse Rate

Supine BP and PR will be measured with the participant's arm supported at the level of the heart and recorded to the nearest mm Hg after approximately 5 minutes of rest. The same arm (preferably the dominant arm) will be used throughout the study. Participants should be instructed not to speak during measurements. BP and PR assessments will be performed after collection of ECGs and prior to collection of blood draws if scheduled at the same time.

The same properly sized and calibrated BP cuff will be used to measure BP each time. The use of an automated device for measuring BP and pulse rate is acceptable; however, when done manually, pulse rate will be measured in the brachial/radial artery for at least 30 seconds. When the timing of these measurements coincides with a blood collection, BP and pulse rate should be obtained prior to the nominal time of the blood collection.

Additional collection times, or changes to collection times, of BP and pulse rate will be permitted, as necessary, to ensure appropriate collection of safety data. If the pulse rate is outside of the normal limits, respiratory rate will also be collected.

Any untoward vital sign findings that are identified during the active collection period and meet the definition of an AE or SAE ([Appendix 3](#)) must be reported according to the processes in Sections [8.4.1](#) to [8.4.3](#).

8.3.2.2. Respiratory Rate

RR will be collected if the PR is outside of normal range. Respiratory rate will be measured after approximately 5 minutes of rest in a supine position by observing and counting the respirations of the participant for 30 seconds and multiplying by 2.

8.3.2.3. Temperature

Temperature will be measured orally. No eating, drinking, or smoking is allowed for 15 minutes prior to the measurement. Temperature will be measured as per CRU standard practice.

8.3.3. Electrocardiograms

Standard 12-lead ECGs utilizing limb leads (with a 10-second rhythm strip) should be collected at times specified in the **SoA** section of this protocol using an ECG machine that automatically calculates the HR and measures PR interval, QT interval, QTcF, and QRS complex. Alternative lead placement methodology using torso leads (eg, Mason-Likar) should not be used given the potential risk of discrepancies with ECGs acquired using standard limb lead placement. All scheduled ECGs should be performed after the participant has rested quietly for at least 5 minutes in a supine position.

TriPLICATE 12-lead ECGs will be obtained approximately 2 to 4 minutes apart; the average of the triplicate ECG measurements collected before dose administration on Day 1 of each period and before the meal for Sequence 1 Period 2, Sequence 2 Period 1, and Period 3 will serve as each participant's baseline QTcF value.

To ensure safety of the participants, a qualified individual at the investigator site will make comparisons to baseline measurements. Additional ECG monitoring will occur if a) the mean value from the triplicate measurements for any postdose QTcF interval is increased by ≥ 60 ms from the baseline **and** is >450 ms; or b) an absolute QT value is ≥ 500 ms for any scheduled ECG. If either of these conditions occurs, then a single ECG measurement must be repeated at least hourly until QTcF values from 2 successive ECGs fall below the threshold value that triggered the repeat measurement.

If a) a postdose QTcF interval remains ≥ 60 ms from the baseline **and** is >450 ms; or b) an absolute QT value is ≥ 500 ms for any scheduled ECG for greater than 4 hours (or sooner, at the discretion of the investigator); or c) QTcF value get progressively longer, the participant should undergo continuous ECG monitoring. A cardiologist should be consulted if QTcF values do not return to less than the criteria listed above after 8 hours of monitoring (or sooner, at the discretion of the investigator).

In some cases, it may be appropriate to repeat abnormal ECGs to rule out improper lead placement as contributing to the ECG abnormality. It is important that leads be placed in the same positions each time in order to achieve precise ECG recordings. If a machine-read QTc value is prolonged, as defined above, repeat measurements may not be necessary if a qualified medical provider's interpretation determines that the QTcF values are in the acceptable range.

ECG values of potential clinical concern are listed in [Appendix 8](#).

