- k. All ECG assessments will be made after at least a 5-minute rest in a supine position and prior to any blood draws or vital sign measurements. Day 4 ECGs are for Period 3 only. Single ECGs are needed for screening, times after the study intervention has been administered, Day 4 of Period 3, and upon early termination/discontinuation, while triplicate ECGs are needed for baseline.

Visit Identifier Abbreviations used in this table may be found in Appendix 10	Screening^a	Periods 1-3^b												Follow-Up	Early Termination/Discontinuation				
		Days Relative to Day 1	Days -28 to -2	Day -1	Day 1								Day 2	Day 3	Day 4	28-35 days^t			
Hours After Dose			0	0.5	1	1.5	2	2.5	3	4	6	8	12	16	24	36	48	72	

- l. Single supine BP and PR will be performed following at least a 5-minute rest in a supine position. BP and PR assessments will be performed after collection of ECGs and prior to collection of blood draws if scheduled at the same time. Day 4 measurements are for Period 3 only. Temperature will be measured as per CRU standard practice. RR will be collected if the PR is outside of normal range.
- m. Full ophthalmic exam will be conducted if treatment emergent ocular AEs are observed.
- n. See Section [8.3.6](#) for details.
- o. PF-07284890 will be administered orally on Day 1 after overnight fasting until the start of study procedures for each treatment period. PF-07284890 will be administered orally and in fasted or fed state according to the conditions described in Protocol Section [5.3.2 Meals and Dietary Restrictions](#).
- p. One (approximately 3 mL) blood sample for PK analysis of PF-07284890 will be taken at the designated time points post dose in each treatment period.
- q. Retained Research Samples Prep D1 for Genetics: If not collected on the designated collection day, collect at the next available time point when biospecimens are being collected in conjunction with a participant visit. These samples will be collected during Period 1 only.
- r. Participants will be discharged on Day 4 of of Period 3 after completion of all assessment.
- s. Collect at pre-dose for all 3 periods. For fed periods (Sequence 2 Period 1 and Sequence 1 Period 2 for the low-fat meal and Period 3 for the high-fat meal), the ECGs should be done before the pre-dose PK sample, and both should be done before the meals.
- t. Contact may occur via telephone and must occur 28 to 35 days from administration of the final dose of study intervention.
- CC1

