7.1.1. ECG Changes

A participant who meets either bulleted criterion based on ECG readings will be withdrawn from the study intervention.

- QTcF >500 ms.
- Change from baseline: QTcF >60 ms and QTcF >450 ms.

If a clinically significant finding is identified (including, but not limited to, changes from baseline in QTcF after enrollment), the investigator or qualified designee will determine if the participant can continue in the study and if any change in participant management is needed. This review of the ECG printed at the time of collection must be documented. Any new clinically relevant finding should be reported as an AE.

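### The QTcF-rise trigger for hourly repeat ECGs needs post-dose triplicates, but only single ECGs are scheduled after dosing

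*Protocol*

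**What the plan says.** Protocol Section 8.3.3 sets two conditions for additional ECG monitoring:

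- (a) "the mean value from the triplicate measurements for any postdose QTcF interval is increased by" at least 60 ms from baseline, and the value is above 450 ms;
- (b) the uncorrected QT is at least 500 ms on any scheduled ECG.

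If either is met, "a single ECG measurement must be repeated at least hourly until QTcF values from 2 successive ECGs fall below the threshold value" that set off the repeats. A further step, continuous monitoring, applies if "a postdose QTcF interval remains" beyond the same limits, if QT stays at 500 ms or more for over 4 hours, or if QTcF keeps lengthening.

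Footnote k of the Schedule of Activities (Protocol Section 1.3) fixes how many tracings are taken: "Single ECGs are needed for screening, times after the study intervention has been administered, Day 4 of Period 3", and at early termination, "while triplicate ECGs are needed for baseline". The triplicate row of the schedule has one mark. Footnote s places it pre-dose in each of the three periods.

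**The concern.** Condition (a) tests a quantity that the schedule never produces. A site that follows the text exactly would have only one value at each post-dose time, no triplicate mean to compare with baseline, and so no instruction to start hourly repeats after a QTcF rise of 60 ms or more to above 450 ms.

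The stake is participant safety; the PK comparison is untouched. The participants are healthy and gain no clinical benefit. The risk table in Protocol Section 2.3.1 lists cardiac conduction changes among the risks of approved BRAF inhibitors and names ECGs as the mitigation. Section 4.2.1 allows for exposure up to about two-fold higher after the high-fat meal in Period 3. A mandatory monitoring rule should be workable with the ECGs that are actually scheduled.

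**Working it through.** The documents give no figure to reproduce on this point. The check has three parts.

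**1. Does any scheduled post-dose ECG supply a triplicate mean?** No. Footnote k makes the post-dose ECGs single, and footnote s puts the only triplicate before dosing. Section 8.3.3 does not ask for a confirmatory triplicate, and the repeats it orders are themselves single. The replicate rule in Protocol Section 9.3.2.1 and SAP Section 3.5.4 applies only if more than one ECG happens to be taken at a nominal time. It is an analysis convention and schedules nothing.

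**2. Does condition (b) catch the same cases?** SAP Section 3.5.4 gives QTcF = QT / RR^(1/3), with RR = 60/HR. Setting QT = 500 ms:

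- Heart rate at or below which condition (b) is met for a given QTcF: HR = 60 × (QTcF/500)³.
- QTcF needed to meet condition (b) at a given heart rate: QTcF = 500 × (HR/60)^(1/3).

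| QTcF (ms) | Condition (b) met only at or below (bpm) |
|---|---|
| 450 | 60 × 0.729 = 43.7 |
| 460 | 46.7 |
| 480 | 53.1 |
| 500 | 60.0 |

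| Heart rate (bpm, assumed) | QTcF when QT = 500 ms (ms) |
|---|---|
| 50 | 470.5 |
| 60 | 500.0 |
| 70 | 526.4 |
| 80 | 550.3 |
| 90 | 572.4 |

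At 70 bpm, for example, a participant whose QTcF has risen by 60 ms or more to a value above 450 ms but below 526 ms meets the intended condition (a) and not condition (b).

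**3. Would a single-ECG trigger raise too many false alarms?** The documents give no within-participant QTcF SD, so I assume 8 to 15 ms and a normal distribution. With no credit for averaging the baseline, the SD of a change is √2 × SD.

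| SD (ms) | SD of change (ms) | P(chance rise ≥60 ms) per ECG |
|---|---|---|
| 8 | 11.3 | 0.00000006 |
| 10 | 14.1 | 0.00001 |
| 12 | 17.0 | 0.0002 |
| 15 | 21.2 | 0.0023 |

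These probabilities are before the further requirement that QTcF exceed 450 ms. If replicates are independent with SD s, the change from a triplicate-mean baseline has SD s√(1 + 1/3) = 1.155s for a single post-dose ECG and s√(1/3 + 1/3) = 0.816s for a post-dose triplicate mean. The single-ECG trigger is therefore about 1.155/0.816 = 1.41 times as noisy, which is tolerable given the table.

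**The case against.** The strongest reply is that the intent is plain and other text protects participants.

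- The continuous-monitoring paragraph uses the same thresholds on a post-dose QTcF without mentioning triplicates.
- The later sentence "If a machine-read QTc value is prolonged, as defined above, repeat measurements may not be necessary" suggests that repeats are the default after one prolonged machine-read value.
- Section 7.1.1 withdraws a participant from study intervention for QTcF above 500 ms, or for "Change from baseline: QTcF >60 ms and QTcF >450 ms". It adds, for a clinically significant finding, that "This review of the ECG printed at the time of collection must be documented".
- Appendix 8 lists a QTcF rise of 60 ms or more as a possible adverse event, and recorded events must be followed up.
- Participants are confined to the unit, and staff compare ECGs with baseline.
- The heart-rate table shows where condition (b) is silent. It does not show how often a true 60 ms rise would occur, and Section 2.2.3 reports no significant in vivo safety pharmacology findings.

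Much of this stands. A large rise would probably be noticed, most sites would guess the intended reading, and the frequency of a qualifying rise is unknown. What remains is that none of these provisions removes the triplicate condition or orders the hourly repeats. Withdrawal under Section 7.1.1 can only stop a later dose, and after Period 3 none is left. Continuous monitoring is an escalation that presupposes serial ECGs already under way. The machine-read sentence relies on a definition given earlier in the section, whose first step is condition (a), and its function is to waive repeats. Appendix 8 concerns event reporting, not ECG frequency.

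**Conclusion.** The concern holds. As written, the QTcF-change trigger cannot be evaluated on any scheduled post-dose ECG, and the uncorrected-QT trigger does not replace it at ordinary resting heart rates. The textual conflict is certain. The heart-rate cut-offs follow from the SAP's own formula; the resting range of 50 to 90 bpm and the SD range of 8 to 15 ms are assumptions. The practical consequence is limited: the hourly repeats depend on the site inferring what was meant, while several backstops make outright non-detection unlikely. This is a minor safety-rule correction that should be made. It has no bearing on the food-effect estimates.

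**What to change.** In Protocol Section 8.3.3, reword condition (a) so that it applies to any scheduled single post-dose QTcF that is at least 60 ms above the pre-dose triplicate-mean baseline and above 450 ms, optionally confirmed by a repeat ECG. If the sponsor prefers to keep a triplicate basis, a workable alternative is to require a confirmatory triplicate whenever a single ECG crosses those limits.

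The recommended wording is a one-phrase edit and adds no visit or scheduled ECG. Its price is an occasional chance alarm, at most about 0.2% per ECG at the highest assumed SD, which the optional repeat can clear.

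As clerical tidying in the same amendment, Protocol Section 9.3.2.1 should measure change from the pre-dose triplicate mean in place of a single pre-dose ECG. Section 8.3.3 and SAP Section 3.5.4 already use the triplicate mean, so the planned tables do not change.

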8.4.3. Follow-Up of AEs and SAEs

After the initial AE or SAE report, the investigator is required to proactively follow each participant at subsequent visits/contacts. For each event, the investigator must pursue and obtain adequate information until resolution, stabilization, the event is otherwise explained, or the participant is lost to follow-up (as defined in Section 7.3).

In general, follow-up information will include a description of the event in sufficient detail to allow for a complete medical assessment of the case and independent determination of possible causality. Any information relevant to the event, such as concomitant medications and illnesses, must be provided. In the case of a participant death, a summary of available autopsy findings must be submitted as soon as possible to Pfizer Safety.

Further information on follow-up procedures is provided in [Appendix 3](#).

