9.3.2.1. Electrocardiogram Analyses

Changes from baseline for the ECG parameters HR, QTcF, PR interval, and QRS complex will be summarized by treatment and time. The frequency of uncorrected QT values above 500 ms will be tabulated.

The number (%) of participants with maximum postdose QTcF values and maximum increases from baseline in the following categories will be tabulated by treatment:

Safety QTcF Assessment

Degree of Prolongation	Mild (ms)	Moderate (ms)	Severe (ms)
Absolute value	>450-480	>480-500	>500
Increase from baseline		30-60	>60

If more than 1 ECG is collected at a nominal time after dose administration (for example, triplicate ECGs), the mean of the replicate measurements will be used to represent a single observation at that time point. If any of the 3 individual ECG tracings has a QTcF value >500 ms, but the mean of the triplicates is not >500 ms, the data from the participant's individual tracing will be described in a safety section of the CSR in order to place the >500 -ms value in appropriate clinical context. However, values from individual tracings within triplicate measurements that are >500 ms will not be included in the categorical analysis unless the average from the triplicate measurements is also >500 ms. Changes from baseline will be defined as the change between the postdose QTcF value and the predose single ECG value on Day 1.

CCI

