- For each AE or SAE, the investigator **must** document in the medical notes that they have reviewed the AE or SAE and have provided an assessment of causality.
- There may be situations in which an SAE has occurred and the investigator has minimal information to include in the initial report to the sponsor. However, **it is very important that the investigator always make an assessment of causality for every event before the initial transmission of the SAE data to the sponsor.**
- The investigator may change their opinion of causality in light of follow-up information and send an SAE follow-up report with the updated causality assessment.
- The causality assessment is one of the criteria used when determining regulatory reporting requirements.
- If the investigator does not know whether or not the study intervention caused the event, then the event will be handled as “related to study intervention” for reporting purposes, as defined by the sponsor. In addition, if the investigator determines that an SAE is associated with study procedures, the investigator must record this causal relationship in the source documents and CRF, and report such an assessment in the dedicated section of the CT SAE Report Form and in accordance with the SAE reporting requirements.

Follow-Up of AEs and SAEs

- The investigator is obligated to perform or arrange for the conduct of supplemental measurements and/or evaluations, as medically indicated or as requested by the sponsor, to elucidate the nature and/or causality of the AE or SAE as fully as possible. This may include additional laboratory tests or investigations, histopathological examinations, or consultation with other healthcare providers.
- If a participant dies during participation in the study or during a recognized follow-up period, the investigator will provide Pfizer Safety with a copy of any postmortem findings, including histopathology.

- New or updated information will be recorded in the originally submitted documents.
- The investigator will submit any updated SAE data to the sponsor within 24 hours of receipt of the information.

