10.8. Appendix 8: ECG Findings of Potential Clinical Concern

ECG Findings That May Qualify as AEs

Marked sinus bradycardia (rate <40 bpm) lasting minutes.New PR interval prolongation >280 ms.New prolongation of QTcF to >480 ms (absolute) or by ≥ 60 ms from baseline.New-onset atrial flutter or fibrillation, with controlled ventricular response rate: ie, rate <120 bpm.New-onset type I second-degree- (Wenckebach) AV block of >30 seconds' duration.Frequent PVCs, triplets, or short intervals (<30 seconds) of consecutive ventricular complexes.
ECG Findings That May Qualify as SAEs

QTcF prolongation >500 ms.New ST-T changes suggestive of myocardial ischemia.New-onset LBBB (QRS complex >120 ms).New-onset right bundle branch block (QRS complex >120 ms).Symptomatic bradycardia.Asystole:
In awake, symptom-free participants in sinus rhythm, with documented periods of asystole ≥ 3.0 seconds or any escape rate <40 bpm, or with an escape rhythm that is below the AV node.In awake, symptom-free participants with atrial fibrillation and bradycardia with 1 or more pauses of at least 5 seconds or longer.Atrial flutter or fibrillation, with rapid ventricular response rate: rapid = rate >120 bpm.Sustained supraventricular tachycardia (rate >120 bpm) ("sustained" = short duration with relevant symptoms or lasting >1 minute).Ventricular rhythms >30 seconds' duration, including idioventricular rhythm (HR <40 bpm), accelerated idioventricular rhythm (HR >40 bpm to <100 bpm), and

monomorphic/polymorphic ventricular tachycardia (HR >100 bpm [such as torsades de pointes]).

- Type II second-degree (Mobitz II) AV block.
- Complete (third-degree) heart block.

ECG Findings That Qualify as SAEs

- Change in pattern suggestive of new myocardial infarction.
- Sustained ventricular tachyarrhythmias (>30 seconds' duration).
- Second- or third-degree AV block requiring pacemaker placement.
- Asystolic pauses requiring pacemaker placement.
- Atrial flutter or fibrillation with rapid ventricular response requiring cardioversion.
- Ventricular fibrillation/flutter.
- At the discretion of the investigator, any arrhythmia classified as an adverse experience.

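### The 500 ms trigger for hourly ECGs in Protocol 8.3.3 uses uncorrected QT, so a rare participant whose QTcF above 500 ms requires withdrawal meets no mandatory trigger for repeat ECGs

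*Protocol*

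**What the plan says.** **Hourly repeats (Protocol 8.3.3).** There are two triggers. Trigger (a) is a postdose QTcF, worded as a mean of triplicates, that is at least 60 ms above baseline and above 450 ms. Trigger (b) is an absolute QT of at least 500 ms on any scheduled ECG. Once either is met, "then a single ECG measurement must be repeated at least hourly until QTcF values from 2 successive ECGs fall below the threshold value" that started the repeats. The next paragraph escalates to continuous monitoring. It again puts the 500 ms limb on QT, and adds a limb for QTcF that keeps lengthening.

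**Waiver (same section).** "If a machine-read QTc value is prolonged, as defined above, repeat measurements may not be necessary" if a qualified provider finds QTcF acceptable.

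**Withdrawal (Protocol 7.1.1).** The criteria are QTcF above 500 ms, or a QTcF change above 60 ms with QTcF above 450 ms. "A participant who meets either bulleted criterion based on ECG readings will be withdrawn from the study intervention".

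**Type of ECG (Protocol 1.3, footnote k).** "Single ECGs are needed for screening, times after the study intervention has been administered, Day 4 of Period 3, and upon early termination/discontinuation". Triplicates are for baseline only.

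**QT and QTcF as separate quantities.** Section 8.3.3 lists both as machine outputs. Section 9.3.2.1 categorises QTcF and separately states: "The frequency of uncorrected QT values above 500 ms will be tabulated". Appendix 8 lists "QTcF prolongation >500 ms" among findings that may qualify as SAEs.

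**The concern.** The protocol treats QTcF above 500 ms as its severe category (9.3.2.1), a possible SAE (Appendix 8) and a reason for withdrawal (7.1.1). One would expect it to start the mandatory repeat ECGs by itself. It does not, because the 500 ms limb of 8.3.3 is on uncorrected QT. At heart rates above 60 bpm, QT is shorter than QTcF, so QTcF can pass 500 ms while QT stays below it.

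The order of severity is then inverted. A QTcF of 455 ms after a 60 ms rise mandates hourly ECGs, while a QTcF of 505 ms after a 59 ms rise at 75 bpm does not. Withdrawal prevents the next dose but does nothing about the dose already taken. In the first-in-human study the median Tmax at 200 mg on Cycle 1 Day 1 was 6.0 hours (Protocol Table 4). At stake is how closely one healthy volunteer is watched in those hours. The food-effect estimates do not depend on it.

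**Working it through.** The plan states no figure to reproduce, so the check compares the two rules.

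**Inputs.** Withdrawal criteria from Protocol 7.1.1; triggers (a) and (b) from Protocol 8.3.3; Fridericia correction from SAP 3.5.4, QTcF = QT / RR^(1/3) with RR = 60/HR, so QT = QTcF × (60/HR)^(1/3). Trigger (a) is applied to the single postdose ECG, which is the reading that keeps the gap smallest.

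**Step 1: when is withdrawal met with no trigger?** The change criterion of 7.1.1 (rise above 60 ms, QTcF above 450 ms) always satisfies trigger (a). The gap can therefore come only from QTcF above 500 ms, with both of these:
- (a) fails: rise under 60 ms, so baseline is above 500 − 60 = 440 ms.
- (b) fails: QT under 500 ms, so HR > 60 × (QTcF/500)³.

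**Step 2: example.** Baseline 446 ms, QTcF 505 ms, 75 bpm.
- Rise = 505 − 446 = 59 ms, so (a) is not met.
- QT = 505 × (60/75)^(1/3) = 468.8 ms, so (b) is not met.
- QTcF is above 500 ms, so 7.1.1 is met.

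**Step 3: extent.** For a given baseline, the gap in whole milliseconds runs from QTcF 501 to baseline + 59.

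| Baseline QTcF (ms) | QTcF in the gap (ms) | HR needed at upper end (bpm) |
|---|---|---|
| 442 | 501 | 60 × (501/500)³ = 60.4 |
| 449 | 501–508 | 60 × (508/500)³ = 62.9 |
| 455 | 501–514 | 60 × (514/500)³ = 65.2 |
| 460 | 501–519 | 60 × (519/500)³ = 67.1 |

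Exclusion criterion 11 gives QTcF of 450 ms or more as an example of an excluding finding, but that is an eligibility test. The baseline in 8.3.3 is the Day 1 predose triplicate mean of each period, and no ceiling is stated for it. The upper end is therefore open.

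**Step 4: frequency.** The documents give no QTcF distribution, so this rests on assumption. The simulation used baseline QTcF with mean/SD from 405/15 to 415/20 ms, truncated at 450 ms; a mean postdose rise of 0 to 30 ms; mean HR of 62 or 68 bpm; and 10 postdose ECGs per participant. The expected number ever in the gap was 0.00 to 0.07 of 12. The top value needs a 30 ms mean rise, which nothing in the documents suggests. The truncation at 450 ms pulls the other way, so these counts are somewhat low if a period's baseline can exceed it.

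**Step 5: the rule after the change.** With QTcF of 500 ms or more added, any QTcF above 500 ms fires it. A rise above 60 ms with QTcF above 450 ms fires (a), once (a) covers single ECGs. Every 7.1.1 withdrawal then triggers repeats, and nothing that now triggers is lost. Replacing QT by QTcF would also close the gap, but limb (b) would no longer fire for slow heart rates: QT 500 ms corresponds to QTcF 485.7, 470.5 and 454.3 ms at 55, 50 and 45 bpm.

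**The case against.** The strongest reply is that nobody in this position would go unwatched. The participant is withdrawn and confined to the unit. Section 7.1.1 requires review of clinically significant ECG findings, 8.1 requires immediate discussion of safety issues with the sponsor, 8.3 allows unscheduled measurements, 4.1 allows a longer stay, and the schedule includes an ECG at discontinuation. If the event is recorded as an AE, "the investigator must pursue and obtain adequate information until resolution, stabilization, the event is otherwise explained" (8.4.3), and the investigator is "obligated to perform or arrange for the conduct of supplemental measurements and/or evaluations, as medically indicated or as requested by the sponsor" (10.3.3). All of this stands and keeps the weight low. None of it mandates hourly ECGs, and the limb for lengthening QTcF would miss a stable 505 ms. The documents therefore do not support inferring that the participant would be left unmonitored, only that the automatic rule does not fire.

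Three other stronger readings are tempting.

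- **The exit rule is also defective, because a QT trigger is left on QTcF.** Below 60 bpm a participant triggered at QT 500 ms may already meet the exit. But exclusion criterion 11 has the same pattern (a long uncorrected QT is rate-corrected and QTcF decides), and the waiver in 8.3.3 fits it. The exit is a defensible choice.
- **The gap is wide, because (a) needs triplicates that are never scheduled after dosing.** Taken literally, QTcF 520 ms at 75 bpm (QT 482.7 ms) would trigger nothing at any baseline. However, the continuous-monitoring paragraph states the 60 ms limb without triplicates, and 9.3.2.1 averages replicates only where more than one ECG exists. Applying (a) to single ECGs is the more natural reading, though the text should say so.
- **QT is simply a slip for QTcF.** The waiver's reference to QTc as defined above hints at this, but the protocol distinguishes the two elsewhere and tabulates uncorrected QT separately.

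**Conclusion.** The mismatch is real but small. With trigger (a) applied to single postdose ECGs, a participant with baseline QTcF above 440 ms, QTcF just above 500 ms, a rise under 60 ms and heart rate above about 60 bpm must be withdrawn yet meets no mandatory trigger for hourly ECGs. A reader might take the gap to stop at baseline 449 ms and QTcF 508 ms because of the screening limit. The documents do not support that bound, since the Day 1 baseline of each period has no stated ceiling.

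The case should be rare: well under one participant of 12 under the assumptions shown. Protocol 2.2.3 reports no significant in vivo safety pharmacology findings, and 2.2.4.1.2 lists no QT event at 200 mg once or twice daily. The existence of the gap follows from the wording and the Fridericia formula; its frequency rests on assumed distributions. This is a cheap improvement of low priority.

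**What to change.** Make two wording changes in Protocol 8.3.3.

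1. In both the hourly-repeat and the continuous-monitoring paragraphs, keep the QT limb and add: *or an absolute QTcF value is ≥500 ms*.
2. Word trigger (a) so that it applies to the single postdose ECG, or to the mean of replicates when replicates are taken.

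Leave the QTcF-based exit as it is; it works directly for the added limb. Do not replace QT by QTcF, which would remove an existing safeguard at slow heart rates.

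The cost is a text edit. No scheduled ECG is added, since the machine already reports both intervals. The only downside is a few extra unscheduled ECGs in rare cases, and the provider waiver in 8.3.3 remains available.
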